12.4. Appendix 4. Epclusa patient information

12.5. Appendix 5a. Epclusa package insert

12.6. Appendix 5b. Harvoni package insert

12.7. Appendix 6. Birminham Vasculitis Activity Score

12.8. Appendix 7. Health Assessment Questionnaire (HAQ-DI)

12.9. Appendix 8. Visual Analog Scale (VAS)

## PROTOCOL SYNOPSIS

**Study Title:** Efficacy of All-Oral Anti-Viral Therapy for Symptomatic Hepatitis C Virus Infection-Related Cryoglobulinemia

**Clinicaltrials.gov identifier:** NCT02825212

**Study Centers:** One site at the Icahn School of Medicine at Mount Sinai with anticipated referrals from other institutions within the system. The Mount Sinai Health Care System includes:

- Mount Sinai Hospital
- Mount Sinai Beth Israel
- Mount Sinai Saint Luke's Roosevelt

Patients will be identified at these additional sites but will be referred to the Icahn School of Medicine at Mount Sinai where the study will be conducted and the IRB will be based. All visits, as well as clinical and laboratory-based studies will be performed at Mount Sinai Health Care System.

### **Target Population:**

Adults with chronic genotypes 1-6 hepatitis C virus (HCV) infection and cryoglobulinemia.

### **Objectives:**

The **primary objectives** of this study are:

- To assess the efficacy of new direct acting oral antivirals: LDV/SOF FDC (Harvoni®) or SOF/VEL FDC (Epclusa®) in patients with chronic HCV infection and MC, measuring the proportion of subjects who attain SVR at 4 and 24 weeks after cessation of treatment.
- To assess efficacy of new direct acting oral antivirals: LDV/SOF FDC (Harvoni®) or SOF/VEL FDC (Epclusa®) in patients with mixed cryoglobulinemia (MC) secondary to chronic HCV infection:

- A complete response is defined as disappearance of arthropathy or kidney involvement, and/or purpura, and >50% reduction in IgM-RF and cryocrit.
- A partial response is a 10-50% reduction in cryocrit and one (but not all) clinical and laboratory signs of systemic vasculitis.

The **secondary objectives** of this study are:

- To assess immunological response of MC to new direct acting oral antivirals: LDV/SOF (Harvoni®) or SOF/VEL FDC (Epclusa®) treatment measuring:
  - FACS/CyTOF analysis of PBMC to determine the effect of DAA treatment on cell-surface markers or MC
  - analysis of isolated mixed cryoglobulins for localization of viral RNA, the presence of HCV core antigen, C1q protein, C1q binding activity and soluble gC1qR.
  - accumulate kinetic data to address the issues of (a) redistribution of viral RNA and core protein between cryoprecipitable and noncryoprecipitable immune complexes with treatment (27) (b) persistence of cryoglobulins and cryoglobulinemic vasculitis following apparent clearance of virus (13,14,28); and (c) persistence of virus in PBMC or cryoprecipitates following apparent systemic clearance (i.e. occult infection) (29).
- To assess safety and tolerability of new direct acting oral antivirals: LDV/SOF FDC (Harvoni®) or SOF/VEL FDC (Epclusa®) in patients with chronic HCV infection and MC.

**Treatment Duration:**

Subjects that have been enrolled and started treatment under protocol version 1 will continue and complete the planned treatment with LDV/SOF FDC (Harvoni®):

- Treatment-naïve subjects will be treated for 12 weeks
- Treatment-experienced non-cirrhotic subjects will be treated for 12 weeks
- Treatment-experienced compensated cirrhotic subjects will be treated for 24 weeks

Subjects enrolled under protocol version 2 will receive SOF/VEL FDC (Epclusa®):

- Treatment-naïve subjects will be treated for 12 weeks
- Treatment-experienced non-cirrhotic subjects will be treated for 12 weeks

- Treatment-experienced compensated cirrhotic subjects will be treated for 12 weeks

**Study Design:** 10 patients with chronic HCV infection and mixed cryoglobulinemia will be treated with new direct acting oral antivirals:

- Ledipasvir/Sofosbuvir 90mg/400 mg FDC once daily for 12 weeks (naïve subjects, non-cirrhotic treatment experienced subjects) or 24 weeks (treatment experienced subjects with compensated cirrhosis) for genotype 1 subjects already enrolled in protocol version 1.
- Sofosbuvir/Velpatasvir 400mg/100mg 400mg/100mg FDC once daily for 12 weeks (naïve subjects, non-cirrhotic treatment experienced or treatment experienced subjects with compensated cirrhosis) for genotype 1-6 subjects enrolled in protocol version 2.

We anticipate that approximately 20% of subjects may have cirrhosis.

**Diagnosis and Main Eligibility Criteria:**

Chronic genotypes 1-6 HCV infected, male and non-pregnant female subjects, ages 18 or older with cryoglobulinemia.

Refer to Sections 4.2 and 4.3 for detailed Inclusion and Exclusion Criteria.

**Study Procedures/Frequency:**

Screening assessments will be completed within 30 days of the Baseline/Day 1 visit. The screening window can be extended to 42 days for subjects requiring liver biopsy or additional HCV genotype testing.

All subjects will complete the following study visits: Screening, Baseline/Day 1, on-treatment visits at the end of Weeks 2, 4, 8 and 12 . Subjects who were already enrolled in the study and receiving 12 weeks treatment with Harvoni® will complete the same visits and schedule of events as subjects receiving Epclusa® (detailed in the current protocol version 2). Subjects that receiving 24 weeks treatment with Harvoni® will also complete treatment visits at week 20 and 24. All subjects will complete the post treatment Week 4, 12 and 24 visits.

Screening assessments will include physical examination, medical history, height, weight, vital signs, 12-lead ECG, adverse events related to screening procedures,

concomitant medications, safety laboratory tests (including hematology, chemistry, and coagulation), HCV genotype and HCV RNA, serology (HIV, HCV, HBV), assessment of the presence or absence of cirrhosis, screening for hepatocellular carcinoma if cirrhosis is present, serum  $\beta$ -hCG (females of child bearing potential only), IL28B genotyping, urinalysis, analysis of cryoglobulinemia measuring cryoglobulins, analyzing cross reactive idiotypes, analysis of complement, HCV core ELISA and FACS (appendix 1).

On-treatment assessments include adverse events (AEs), concomitant medications, study medication pill count, physical examination, weight, vital signs, safety laboratory tests (hematology, chemistry, coagulation), HCV RNA (after Baseline/Day1), urine pregnancy tests (females of child bearing potential only), urinalysis, analysis of cryoglobulinemia measuring cryoglobulins, analyzing cross reactive idiotypes, analysis of complement, HCV core ELISA and clonality/lymphoproliferation / FACS (appendix 1).

Post treatment assessments include AEs, concomitant medications, vital signs, safety laboratory tests, HCV RNA, urine pregnancy tests (females of child bearing potential only) and analysis of cryoglobulinemia measuring cryoglobulins, analyzing cross reactive idiotypes, analysis of complement, HCV core ELISA and clonality/lymphoproliferation / FACS (appendix 1).

#### **Test Product, Dose, and Mode of Administration:**

- Ledipasvir/Sofosbuvir (HARVONI®) is manufactured as a 90mg/400 mg FDC tablet for oral administration. Subjects will take 1 tablet daily with or without food.
- SOF/VEL FDC (Epclusa®) is manufactured as a 400 mg / 100 mg FDC tablet for oral administration. Subjects will take 1 tablet daily with or without food.

#### **Evaluation Criteria:**

- Efficacy:
  - Efficacy of treatment on MC will be assessed as follows:
    - Complete response is defined as disappearance of arthropathy or kidney involvement, and/or purpura, and >50% reduction in IgM-RF and cryocrit.
    - Partial response is a 10-50% reduction in cryocrit and one (but not all) clinical and laboratory signs of systemic vasculitis.

- Efficacy of treatment on HCV infection will be evaluated using scheduled assessments of HCV RNA performed using COBAS® TaqMan® HCV Test, v2.0 for use with Ampliprep.
- Safety: AEs and laboratory tests will be collected throughout the study.

**Statistical Methods:**

This is a pilot study in which 10 patients will be enrolled to explore the efficacy of all-oral anti-viral therapy for symptomatic hepatitis C virus infection-related cryoglobulinemia.

With 10 patients in the study we will be able to estimate the rate of patients who obtain an SVR with a margin of error of approximately 15%.

We will use frequency table and 95% confidence interval to describe the rate of SVR in the total sample and the two subgroups of interest.

Results will be compared to previous published studies (28), as well as unpublished experience, that have delineated the natural history of type 2 cryoglobulinemia, and the response to immunomodulatory therapies, including IFN/Peg-IFN, Ribavirin and Rituximab (27).

***This study will be conducted in accordance with the guidelines of Good Clinical Practice (GCP)***

## **GLOSSARY OF ABBREVIATIONS AND DEFINITION OF TERMS**

ACR American College of Rheumatology  
AE Adverse event  
ALT Alanine aminotransferase  
AST Aspartate aminotransferase  
BW Body weight  
CLcr Creatinine Clearance  
CR complete response  
CRF case report form(s)  
DAAs Direct-acting antiviral agents  
eCRF Electronic case report form(s)  
EOT end of treatment  
ET early termination  
EU European Union  
EudraCT European clinical trials database  
FDA (United States) Food and Drug Administration  
FLC Free Light Chain  
GCP Good Clinical Practice (Guidelines)  
HAQ Health Assessment Questionnaire  
HBV Hepatitis B virus  
HCC Hepatocellular carcinoma  
HCV Hepatitis C virus  
HDPE high density polyethylene  
HIV human immunodeficiency virus  
ICH International Conference on Harmonisation  
IFN Interferon  
IL28B Interleukin 28B gene  
IND Investigational New Drug (Application)  
IRB Institutional review board  
IU International unit  
LDV Ledipasvir

LLoQ Lower limit of quantification  
MAb monoclonal antibody  
MC Mixed cryoglobulinemia  
mL Milliliter  
MPGN membranoproliferative glomerulonephritis  
N Number  
NHL Non-Hodgkins Lymphoma  
NSPs non-structural proteins  
PBMC Peripheral blood mononuclear cell  
PEG-IFN Pegylated interferon  
PI Protease inhibitor or principal investigator  
PT Prothrombin time  
RBC Red blood cell count  
RBV Ribavirin  
RNA ribonucleic acid  
Scr serum creatinine  
SAE Serious adverse event  
SOF Sofosbuvir  
SOF/VEL Sofosbuvir/Velpatasvir  
LDV/SOF Ledipasvir/Sofosbuvir  
SUSAR Suspected Unexpected Serious Adverse Reaction  
SVR Sustained virologic response  
ULN upper limit of the normal range  
VEL Velpatasvir  
WBC White blood cell count

## 1. INTRODUCTION

### 1.1. Background

Hepatitis C Virus (HCV) is a major cause of both hepatic and extrahepatic disease. The former includes the spectrum of autoimmune hepatitis extending to cirrhosis, liver failure, and a long-term increased incidence of Hepatocellular Carcinoma. Cryoglobulinemia includes a group of overlapping syndromes (arthropathy, cutaneous vasculitis, nephropathy, sicca syndrome, and neuropathy) and a long-term increased incidence of Non-Hodgkin Lymphoma (NHL) (1). Extrahepatic disease is significantly associated with chronicity and the presence in blood of easily detectable cold-precipitable rheumatoid factors (i.e. mixed cryoglobulins) (2). In addition, rarer organ-specific disease manifestations that may be associated with HCV include cutaneous (lichen planus), neuromuscular (fibromyalgia), hematologic (autoimmune thrombocytopenia), and endocrine (diabetes mellitus) disorders (3). Although the disease burden of HCV has been estimated to be 3-4M for the United States and ~170-180M worldwide, the exact prevalence of extrahepatic HCV is less certain and has only been studied to a limited extent to include countries in which genotype distribution differs from that found in North America, or among populations in the United States (e.g. HIV co-infected persons, the homeless, the incarcerated) known to have an increased prevalence of clinical diseases that may mimic the overlapping syndromes of mixed cryoglobulinemia (MC) noted above. In one study of ~34,000 HCV-positive veterans versus controls, there was an 11-fold increased incidence of cryoglobulinemia, a 7-fold increase in membranoproliferative glomerulonephritis (MPGN), a 20-30% increase in NHL, and a 2-fold increase in lichen planus compared to HCV-negative controls (4). In addition, both the laboratory finding of mixed cryoglobulins and the clinical syndromes of cryoglobulinemic vasculitis may occur with only minimal or no liver pathology, and may be uncovered in the course of evaluations of MPGN, leukocytoclastic vasculitis, rheumatoid-like arthritis, Sjogren's syndrome, or autoimmune neuropathy (5).

We have a long-standing interest in the cryopathies, including early recognition of the prevalence of hepatic disease among patients affected by purpura, arthralgias and MPGN, progression to liver failure in some patients with long-term follow-up (15), characterization of the clonality of the IgMk component of type 2 cryoglobulins, phlogistic activity of mixed cryoglobulins with regard to complement and other mediators

(16), and methodology for the accurate isolation of characterization of cold-precipitable RFs (17). Our current data base includes 180 patients with the syndrome of MC with long-term follow-up of 40 patients spanning 1960-2010. The cohort of MC since the description of HCV in 1989 is 55% female, with an overall incidence of 68% cutaneous disease, 56% arthropathy, 35% nephropathy, 58% neuropathy, 60% type 2/40% type 3 mixed cryoglobulins, and 60% HCV. In addition, we recently completed a retrospective chart review of 51 HCV-positive patients with MC seen at our medical center between 2003-2013, 60% having genotype 1, 14% genotype 2 and 10% genotype 3, in which we specifically analyzed the efficacy of current antiviral therapy and Rituximab in this cohort with regard to progression of liver disease to transplantation and MPGN to end-stage renal disease requiring dialysis (16). This experience may be compared to a very recent report from Italy which noted a ~30% incidence of genotype 2 among their MC patients receiving direct acting antivirals (DAA) treatment (19).

Mount Sinai Health Care System is a major referral center for HCV-infected patients, many of whom are being uncovered as a result of mandated screening, because of our free-standing Hepatology division, specialized HIV, hemophilia, and common variable immunodeficiency patient populations, and our active liver transplantation program. Ongoing clinical studies are testing the efficacy all-oral antiviral therapy in co-infected patients and in post-transplant patients susceptible to recurrence of disease. A review of the morphologic features of extrahepatic disease in this patient population has recently been published from our institution (5). The laboratory of [name] has extensive experience in the performance of the immunologic and rheumatologic procedures and techniques that are proposed. [name] also has extensive experience in performing the clinical assessments for clinical MC. [name] have significant experience in the use of DAAs for HCV, including participation in the ASTRAL-4 study of Sofosbuvir and Velpatasvir for HCV in patients with decompensated cirrhosis (20), and the validation of efficacy of Sofosbuvir and Ledipasvir for recurrent Hepatitis C in liver transplant recipients (21). Lastly, [name] laboratory has published studies of the basic virology of HCV, including hepatitis core antigen, HCV quasi-species, and cell surface markers in established and treated disease.

## **1.2. Rationale for the Current Study**

The treatment of extrahepatic disease manifestations of HCV has largely paralleled that of hepatic disease. Interferon was reported to have efficacy for MC even before linkage of the syndrome to HCV in 1989, and successful combination therapy with ribavirin was found to eliminate virus and lead to the resolution of immunologic abnormalities associated with extrahepatic disease (1). In addition, ~75% of HCV-associated indolent asymptomatic lymphoproliferative diseases remit with successful antiviral therapy (6). However, in many instances, MC (notably cutaneous vasculitis) will relapse with recurrence of virus, and may occasionally persist even after clearance (7). In particular, side effects of Interferon alpha, including the uncovering of frank autoimmune disease, theoretically may mitigate response of extrahepatic disease to treatment (8). Peg-interferon increased the response rate of MC, and decreased the duration of treatment, but side effects remained problematic (1).

An alternative approach to the treatment of MC has been the use of immunomodulatory agents. In particular, B-cell expansion in peripheral blood and in lymphoid follicles in the liver prevalent amongst HCV-infected persons provided a rationale for the use of depletion as a therapeutic strategy. Rituximab (anti-CD20) monotherapy has been used mostly for treatment failures/intolerance or in the setting NHL, and has yielded response rates in the setting of involvement of skin (73%); MPGN (70%); joint (53%); and nerve (36%). However, this monoclonal antibody (MAb) has the potential to form immune-complexes with mixed cryoglobulin RF and cause clinical vasculitis in patients with high cryocrits, and may raise the HCV RNA level in rare patients, causing cytotoxicity. Following Rituximab with Peg-IFN plus ribavirin achieved greater than a 60% complete response (CR) in patients resistant to combination treatment alone (9). Other approaches include the use of Aldesleukin, an inducer of regulatory T-cell activity, MAbs targeted to specific B-cell subsets or costimulatory signal molecules (e.g. BAFF) or agents inhibiting the interaction of HCV core antigen with C1q in cryoprecipitates via the receptor for the globular domain of C1q (gC1qR) (1).

The development of low molecular weight inhibitors of the non-structural proteins (NSPs) elaborated by HCV, in particular 5A, 5B nucleoside and non-nucleoside polymerase inhibitors, and inhibitors of 3/4A serine proteases; to selectively inhibit HCV replication has raised the prospect of “all-oral” treatment for both hepatic and extrahepatic

manifestations of disease. However, the use of first generation direct-acting antiviral agents (Telaprevir® and Boceprevir® linear NS3/4A protease inhibitors) was limited by frequent escape mutants, efficacy restricted to genotype-1, need to retain protocols including PegIFN and ribavirin, potential for significant drug interactions, and serious side effects. In a trial of combination therapy including Telaprevir® for 13 patients with MC, all had significant AEs, including asthenia (92%), anemia (84%), neutropenia and bacterial infection (54%) (10). Approval of an uridine nucleoside analogue that selectively inhibits HCV NS5B RNA-dependent RNA polymerase (Sofosbuvir) by the FDA late 2013 has led to proof-of-concept trials in which combination all-oral therapy has proven effective for both genotype 1 and other genotypes, with a number of other regimens under development. In particular, the combination of Sofosbuvir (SOF) and Ledipasvir (LDV) has been reported to have almost universal efficacy in a 12 week regimen for genotype 1, and the combination of SOF and Ribavirin (RBV) for genotypes 2-6 in a 24 week regimen (11,12). Most recently, the combination of Sofosbuvir and Velpatasvir (SOF/VEL), Epclusa®, has been shown to have pan-genotypic efficacy in pivotal studies (23,24) and is rapidly becoming standard-of care for chronic HCV infection (25). Inclusion of genotypes 1-6 in our study will allow us to correlate possible confounding factors (e.g. specific extra-hepatic disease manifestations, immunoglobulin V-region gene usage; IL28B genotype; HCV Core gene mutations) compared to the published experience for Sofosbuvir and Velpasvir for other genotypes (23,24). It will also allow us to increase enrollment from a diminishing pool of patients who have yet to undergo treatment with 12 week course of Epclusa® (sofosbuvir/velpatasvir) in compensated patients (Child-Pugh A). In addition, persistence of cryoglobulinemia even after viral clearance with the newer regimens has also raised the question of whether longer treatment regimens may be appropriate in the setting of significant extrahepatic disease (13). To date, only limited published experience exists with regard to the “post-viral” phase of HCV MC, consisting of retrospective analyses involving various genotypes and differing regimens of DAAs (19,26). Thus, the timing is right for a prospective trial of all-oral treatment with Epclusa® (SOF/VEL) to rigorously evaluate the effect on extrahepatic disease manifestations in patients with MC of all genotypes, and to re-establish the efficacy of antiviral therapy in halting the direct and indirect role of HCV in driving autoimmune disease and lymphoproliferation. Using an interferon-sparing regimen to treat patients with HCV-related cryoglobulinemia will help answer the

question as to whether immunomodulating therapy plays a role at all in eradicating cryoglobulins long-term, and whether antiviral therapy alone is adequate. If the latter, appreciable morbidity and mortality may be saved in avoiding treating these potentially sick, often cirrhotic patients, with immunomodulatory therapies.

## 2. OBJECTIVES

The **primary objectives** of this study are:

- To assess the efficacy of new direct acting oral antivirals: LDV/SOF FDC (Harvoni®) or SOF/VEL FDC (Epclusa®) in patients with chronic HCV infection and MC, measuring the proportion of subjects who attain SVR at 4 and 24 weeks after cessation of treatment.
- To assess efficacy of new direct acting oral antivirals: LDV/SOF FDC (Harvoni®) or SOF/VEL FDC (Epclusa®) in patients with MC secondary to chronic HCV infection:
  - A **complete response** is defined as disappearance of arthropathy or kidney involvement, and/or purpura, and >50% reduction in IgM-RF and cryocrit.
  - A **partial response** is a 10-50% reduction in cryocrit and one (but not all) clinical and laboratory signs of systemic vasculitis (see below) (33)

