10. Null or partial response to previous therapies for MC, including corticosteroids, cytotoxic agents (cyclophosphamide, azathioprine), hydroxychloroquine, methotrexate, mono- or combination therapy with IFN $\alpha$ /PEG-IFN and ribavirin, and/or CD20 depletion with Rituximab.
- a. Patients can be on ongoing treatment with one of the drugs described above at inclusion unless there is significant DDI.
11. Subjects has the following laboratory parameters at screening:
- a) ALT <10 x the upper limit of normal (ULN)
  - b) AST <10 x ULN
  - c) Adequate bone marrow function as indicated hematologic parameters listed below and/or bone marrow cellularity >60-70% average for age.
    - a. WBC >1500 /uL
    - b. Platelets > 50,000/uL
  - d) Direct bilirubin >2 x ULN
  - e) INR >1.5 x ULN unless subject has known hemophilia or is stable on an anticoagulant regimen affecting INR
12. Females of childbearing potential (as defined in Appendix 3) must have a negative serum pregnancy test at Screening and a negative urine pregnancy test on Baseline/Day 1 prior to treatment.

13. Male subjects and female subjects of childbearing potential who engage in heterosexual intercourse must agree to use protocol specified method(s) of contraception as described in Appendix 3.
14. Lactating females must agree to discontinue nursing before the study drug is administered.
15. Subject must be of generally good health, with the exception of chronic HCV infection, as determined by the Investigator.
16. Subject must be able to comply with the dosing instructions for study drug administration and able to complete the study schedule of assessments.

**Note: Definition of Mixed Cryoglobulinemia** (patients must meet one of the five overlapping syndromes listed below and the presence/documentation of cold-precipitable immune complexes in blood on two different occasions.

- Clinical evidence of cryoglobulinemia, overlapping syndromes:
  1. Cutaneous vasculitis (Raynaud's phenomenon, purpura, skin ulcers, livedo, acrocyanosis)
  2. Glomerulonephritis (hypertension, hematuria, nephrotic syndrome)
  3. Arthropathy (arthralgias, arthritis)
  4. Neuropathy (peripheral and/or central nervous system, distal sensorimotor, mononeuritis multiplex)
  5. Sicca syndrome (xerostomia, xerophthalmia)

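### Complete response names only arthropathy, kidney involvement and purpura, joined by 'or' and 'and/or', so it can be met with another baseline manifestation still active and is undefined for eligible patients who have none of the three

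*Combined protocol and SAP*

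**What the plan says.** Section 2 makes MC response one of two primary objectives. CR "is defined as disappearance of arthropathy or kidney involvement, and/or purpura, and >50% reduction in IgM-RF and cryocrit". The Synopsis gives the same wording under Objectives and under Evaluation Criteria, and adds nothing for other organs. Partial response (PR) "is a 10-50% reduction in cryocrit and one (but not all) clinical and laboratory signs of systemic vasculitis".

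Entry is wider. The note to Section 4.2 says "patients must meet one of the five overlapping syndromes listed below", together with cryoprecipitates documented on two occasions. The five are cutaneous vasculitis, glomerulonephritis, arthropathy, neuropathy and sicca. The skin syndrome is itself broader than purpura: "Cutaneous vasculitis (Raynaud's phenomenon, purpura, skin ulcers, livedo, acrocyanosis".

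The Clinical Responses list in Section 2 says how joints, skin, systemic vasculitis, kidney, nerve and function are measured. It describes neuropathy by symmetry, type and number of extremities, and it omits sicca. Section 6.4.9 has neuropathy and sicca assessed at every visit, with Schirmer and saliva tests and electrophysiology at Screening and post-treatment Week 24. None of this text sets a resolution threshold or ties a result to CR. Section 9 plans a frequency table and confidence interval for SVR only.

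**The concern.** A response called complete would normally mean that the disease the patient brought into the trial has gone. Here the entry list and the response rule do not match. A patient whose purpura clears while nephritis or neuropathy is unchanged can be counted as a complete responder if the two laboratory falls occur. A patient who enters on neuropathy alone has nothing on the CR list to lose.

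The trial is open-label (Section 3.1) with ten patients (Section 4.1), so each classification moves the CR rate by 10 percentage points. Section 9 has no rule for doubtful cases, so they would be settled once results are known. Section 9 also plans to set results beside published responses to immunomodulatory therapy, and Section 1.2 asks whether antiviral therapy alone is adequate. A CR count that can include active organ disease would not answer that question cleanly.

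**Working it through.** The plan states no expected rate, power or precision for CR, so there is no figure to reproduce. Its only precision figure, a margin of about 15%, concerns SVR.

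**Step 1: what the CR sentence accepts.** Let A, K and P mean that arthropathy, kidney involvement and purpura have gone. The sentence can be grouped as (A or K) or P, or as (A or K) and P. Take a patient with all three at baseline, giving 2³ = 8 patterns of clearing:
- (A or K) or P is met in 8 − 1 = 7 patterns.
- (A or K) and P is met in 3 patterns.
- All three have gone in 1 pattern.

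So 6 of the 7, and 2 of the 3, leave a named organ active. If the patient also has neuropathy and sicca there are 2⁵ = 32 patterns. The two groupings are met in 7 × 4 = 28 and 3 × 4 = 12 of them, and everything has gone in 1. These are counts of patterns, not probabilities. They show that neither grouping closes the gap.

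**Step 2: a patient with none of the three.** Take neuropathy only, sicca only or livedo only, each eligible under Section 4.2. If absence counts as disappearance, the clinical half is met at Day 1 and CR rests on the laboratory falls alone. If something must actually disappear, CR can never be met. Sections 2, 6.4.9 and 9 do not choose between these.

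**Step 3: scale.** Section 1.1 gives, for the site's MC cohort, "68% cutaneous disease, 56% arthropathy, 35% nephropathy, 58% neuropathy". It gives no rate for sicca. I count all skin disease as purpura, which understates the share with none of the three named manifestations.

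*Two or more of skin, joint and kidney.* The mean count is 0.68 + 0.56 + 0.35 = 1.59. A patient with at most one contributes at most 1, and any other at most 3, so 1.59 ≤ 1 + 2 × P(two or more). Hence P(two or more) ≥ 0.59/2 = 0.295, whatever the correlation. Under independence:
- none: 0.32 × 0.44 × 0.65 = 0.092
- exactly one: (0.68 × 0.44 × 0.65) + (0.32 × 0.56 × 0.65) + (0.32 × 0.44 × 0.35) = 0.360
- two or more: 1 − 0.092 − 0.360 = 0.548

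*None of the three.* Since 68% have skin disease, the share is at most 1 − 0.68 = 0.32. The three rates sum to more than 1, so it can be 0. Independence gives 0.092. The chance of at least one such patient among ten runs from 0 to 1 − 0.68¹⁰ = 0.98, and is 1 − 0.908¹⁰ = 0.62 under independence.

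*Neuropathy plus at least one of the three.* Lower bound: 0.58 + 0.68 − 1 = 0.26. Upper bound: 0.58. Under independence: 0.58 × 0.908 = 0.527.

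**The case against.** The best defence is the PR definition. By asking for one but not all signs, it suggests that complete response was meant to cover all of them, and the CR sentence may be loose shorthand for whichever manifestation the patient has. That is a fair guess at intent. It does not repair the sentence, which says 'or'. Even the generous reading covers only three manifestations and leaves neuropathy, sicca and non-purpuric skin disease outside.

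A second defence is that other text fills the gap. Part of this stands. PR points to the clinical signs listed after it, which include neuropathy. The Birmingham score has nervous-system and mucous-membrane/eye items, though it is used only in subjects with vasculitis. Skin ulceration is graded within the purpura scale. So a reader who inferred that neuropathy plays no part in any response rule would go too far. The omission is from CR.

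Third, this is a small descriptive pilot with no test or decision resting on CR, and restricting CR to selected organs could be deliberate. Section 1.2 reports rituximab response of 36% for nerve against 73% for skin. That would be a legitimate choice if stated, but the documents do not state it. It would also still leave the 'or' and the patients with none of the three unresolved.

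**Conclusion.** The point holds on the text alone. Under either grouping, CR on a primary objective can be awarded with a baseline manifestation still present, and its clinical half has no defined value for eligible patients with none of the three named manifestations.

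Three stronger readings are not supported:
- A reader might infer that CR cannot be judged in anyone who enters with neuropathy or sicca. A patient with neuropathy plus purpura, arthropathy or nephritis can be classified. The problem there is that the neuropathy is ignored.
- A reader might infer that the CR rate will be overstated. The sentence is ambiguous, and patients with none of the three could be counted either way, so the direction is likely but not certain.
- A reader might take 9% with none of the three, or a 62% chance of at least one in ten, as forecasts. Both rest on independence. The cohort rates alone allow 0% to 32%, and 0% to 98%.

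For scale: at least 29.5% have two or more of skin, joint and kidney disease (55% under independence), 26% to 58% have neuropathy plus a named organ (53%), and 0% to 32% have none of the three (9%). The cohort is only 60% HCV, whereas the trial takes HCV patients with null or partial response to earlier MC therapy. The figures show who could be affected, not how many would be misclassified.

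**What to change.** In the Synopsis and Section 2, reword the clinical half of CR so that every MC manifestation among the five entry syndromes that was present before treatment has disappeared, and no new one has appeared. With it:
- Fix one timepoint. Post-treatment Week 24 is the natural one, because all the organ assessments are scheduled then.
- Use Baseline/Day 1 as the reference, except for Schirmer, saliva and electrophysiology, which are done at Screening and not at Day 1.
- State in advance what counts as disappearance of neuropathy and of sicca on the assessments already scheduled. No threshold exists now, and without one the new wording would be as open as the old.
- Report patients whose only manifestation is neuropathy, sicca or non-purpuric skin disease on a separate line.

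The cost is wording and two thresholds, with no new assessment. The CR rate will probably be lower, though it could rise if patients with none of the three would otherwise count as never meeting CR. One knock-on effect needs settling at the same time. PR as worded applies to a cryocrit fall of 10% to 50%, so a patient with a larger fall and one organ still active would leave CR without entering PR.
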